Exclusion Criteria: 1) Presence of metallic objects or neurostimulators in the brain (including the following: cochlear implants, implanted electrodes/stimulators such as deep brain stimulators and vagus nerve stimulators, aneurysm clips or coils, stents, bullet fragments, jewelry and hair barrettes), 2) pregnancy, 3) history of active seizures or epilepsy, 4) patients with severe scoliosis or other gait impairment that will preclude them from participating in gait evaluation.

Enrollment: Our target is to enroll 10 total patients in the study in a crossover design, with all 10 patients receiving both active and sham rTMS in blinded, random order. In order to enroll 10, we will need to screen more than that number. We anticipate that we will need to screen 20 patients in order to find 10 that are eligible for enrollment. Of those 20, we anticipate that 10 will enroll but later choose not participate in the study.

IRB202101156 6/17/22 IRB approved informed consent will be obtained. The study procedures will be explained, and subjects will have a detailed medical history and neurological examination. Patients will be randomly assigned to receive either active or sham stimulation first (S1), and will then crossover and switch to the other treatment type during the second session (S2). Patients will have primary and secondary outcome measures performed at three time points: Baseline (T0), following rTMS (T1), and 2 weeks after rTMS (T2) (Figure 1). Patients will have the next round of regularly scheduled botulinum toxin injections during the T2 study visit, after the outcome measures have been obtained. Then the entire study protocol will be performed again but the patients will undergo either active or sham rTMS during S2 (whichever option they were not exposed to during S1). The study protocol will take place over approximately 24 weeks. Details of specific parts of the protocol are included below.

at baseline/9 weeks after BoNT (S1:T0), after the full rTMS protocol (S1:T1), and 2 weeks after rTMS (S1:T2). At the T2 visit, patients will be due for their next round of BoNT and will receive it at that time. Patients will have S2:T0 performed 9 weeks following this round of BoNT and will crossover into either active or sham rTMS (whichever condition they did not undergo in S1). Outcomes will be measured immediately following rTMS (S2:T1) and 2 weeks after rTMS (S2:T2).

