Primary Outcome: Motor symptoms of dystonia will be measured with TWSTRS; a widely accepted composite rating scale for cervical dystonia with subscales for clinical severity, functional disability, and associated pain. We will record videos of subjects at baseline and follow-up time points, which will be scored by two independent blinded raters.

Secondary Outcomes: Non-motor symptoms will be measured as follows: mood with the Beck Depression Inventory (BDI) and cognitive tasks as measured by the Wisconsin Card Sorting Task (WCST) and Trail Making Test (TMT); gait with Zeno walkways system for temporal parameters (stance time, double support time, stride time, and cadence), spatial parameters (stride length, step width, step length, step asymmetry), and the dynamic stability index (ratio between single and double support time)^{4,5}; physiological outcomes will be measured with standard procedures for TMS based MEP, CSP, and SICI²⁵⁻³⁰ and HD-EEG based power of alpha and beta bands during resting state.³¹

Randomization: A random number generator will be used to assign patients to active or sham stimulation during the S1 time period. If the number is even, the patient will be assigned active stimulation. If the number is odd, the patient will be assigned sham stimulation. The study team member who makes these assignments will be aware of which patients are receiving active or sham stimulation but will be different from the blinded reviewer. The blinded reviewer will be unaware of the patient's assignment to active or sham stimulation. Following crossover, the patients will undergo whichever treatment condition (active or sham) they were not exposed to during S1.

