rTMS protocol: rTMS will be delivered using a NeuroStar TMS therapy system (Neuronetics, Malvern, PA). The resting motor threshold (RMT) will be defined as the lowest stimulation intensity required to evoke a 50 μ V potential in a target muscle (i.e. first dorsal interosseus muscle/FDI). A figure of eight coil will be used to deliver the stimulation. Patients will be seated in a comfortable reclined chair. The dPMC target will be defined as 1 cm medial and 2 cm anterior to the site of RMT acquisition.¹¹ The rTMS protocol will be as follows: each session will consist of 1-Hz rTMS over the dPMC for 30 minutes (1800 pulses) at 90% of the RMT. Patients will receive 4 sessions per day for 4 consecutive days with a 10-minute break between each session. Daily duration of the rTMS protocol, including breaks, will last approximately 160 minutes. Constant coil position will be continuously monitored during the experiment. During rTMS, all participants will wear earplugs in order to protect the ears from the acoustic artefact associated with the discharge of the stimulation coil.

Sham protocol: Participants will undergo the same procedure for identifying target location and RMT used in patients receiving real rTMS. Simulated rTMS will be administered using a NeuroStar sham coil, which produces discharge noise and vibration without stimulating the cerebral cortex. This technique has been suggested to provide more effective blinding compared to other methods use in previous controlled studies.¹⁷ Although the physician administering TMS will be aware of the status of the subject in terms of real TMS versus sham TMS, this physician will play no role in any of the outcome measures, and will not be present during any of the outcome measure assessments. Similarly, the investigator who performs the outcome measures will not be present during any of the TMS sessions, and therefore will remain blinded to the status of the patients with respect to real rTMS versus sham rTMS.

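### Treatment order is set by an unrestricted even/odd draw, so a 10-patient crossover may well end with unequal sequences, and the SAP names no period term to absorb the imbalance

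*Protocol*

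**What the plan says.** The Protocol's Enrollment section gives the size and design: "Our target is to enroll 10 total patients in the study in a crossover design". On the order of treatments it says only that this will be done "with all 10 patients receiving both active and sham rTMS in blinded, random order". It states no ratio between the two orders.

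The Randomization section gives the mechanism: "A random number generator will be used to assign patients to active or sham stimulation during the S1 time period". The rule is then "If the number is even, the patient will be assigned active stimulation. If the number is odd, the patient will be assigned sham stimulation". Session 2 takes whichever condition was not given in session 1. No block, balance constraint, advance list or concealment step is mentioned.

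On who knows what, the same section says "The study team member who makes these assignments will be aware of which patients are receiving active or sham stimulation", adds that this person differs from the blinded reviewer, and states "The blinded reviewer will be unaware of the patient's assignment to active or sham stimulation". The Sham protocol section says of the physician giving TMS that "this physician will play no role in any of the outcome measures, and will not be present during any of the outcome measure assessments".

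The SAP names a two-way repeated measures ANOVA. It does not name the two factors and does not mention period, sequence or randomization.

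**The concern.** In a two-period crossover, equal sequence groups do two things. They make the period-adjusted treatment contrast as precise as the sample size allows, and they make an additive period effect cancel from the simple active-minus-sham mean. An unrestricted draw over 10 patients guarantees neither.

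A period effect is plausible here. The two sessions follow different botulinum toxin injections about 12 weeks apart. The cognitive tests are repeated at six timepoints. Patients are also selected for short benefit over two consecutive cycles. With no period term named in the SAP, a chance imbalance could enter the estimate as bias, and there are no spare patients to dilute it.

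A second, smaller matter is that the Protocol does not say how an upcoming order is concealed, or whether it is drawn before or after the S1:T0 measures.

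**Working it through.** **Inputs.** N = 10, each patient receiving both conditions (Protocol, Enrollment). Order is by number parity (Protocol, Randomization). The generator's range is not given, so I assume independent draws with probability 0.5 each. The documents state no power, alpha or sequence ratio, so there is no figure of theirs to reproduce.

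**Step 1: the split.** The number assigned active-first is Binomial(10, 0.5), with 2^10 = 1024 equally likely outcomes.

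**Step 2: precision if period is modelled.** The contrast averages the two sequence-group means of the within-patient difference, so its variance is proportional to 1/n1 + 1/n2. At 5:5 this is 0.4. The ratio is (1/n1 + 1/n2)/0.4; for example, at 7:3 it is (1/7 + 1/3)/0.4 = 1.19.

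**Step 3: bias if period is not modelled.** Let the treatment effect be τ and the period effect (session 2 minus session 1) be π. Active minus sham has mean τ − π in active-first patients and τ + π in sham-first patients. The overall mean is τ + π(n2 − n1)/N, so the share of π that enters is |n1 − n2|/10.

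| Split | Outcomes of 1024 | Probability | Variance ratio (period modelled) | Share of period effect (not modelled) |
|---|---|---|---|---|
| 5:5 | 252 | 24.6% | 1.00 | 0 |
| 6:4 | 420 | 41.0% | 1.04 | 0.2 |
| 7:3 | 240 | 23.4% | 1.19 | 0.4 |
| 8:2 | 90 | 8.8% | 1.56 | 0.6 |
| 9:1 | 20 | 2.0% | 2.78 | 0.8 |
| 10:0 | 2 | 0.2% | not estimable | 1.0 |

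Cumulatively, 7:3 or worse is 352/1024 = 34.4%, and 8:2 or worse is 112/1024 = 10.9%. A split of 6:4 or better is 672/1024 = 65.6%.

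**Step 4: averages.** Over the 1022 outcomes with both sequences present, the mean variance ratio is (252×1 + 420×1.0417 + 240×1.1905 + 90×1.5625 + 20×2.7778)/1022 = 1171.4/1022 = 1.146. That corresponds to 10/1.146 = 8.7 effective patients. The total excess is 1171.4 − 1022 = 149.4, of which 8:2 and 9:1 supply 90×0.5625 + 20×1.7778 = 86.2, or 58%. The mean absolute share of a period effect entering an unadjusted contrast is (84 + 96 + 54 + 16 + 2)/1024 = 0.25.

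**Step 5: does timing of the draw matter?** Under independent draws, if leaving is unrelated to order, the 10 treated patients remain Binomial(10, 0.5) whenever the draw is made. Under a balanced list it does matter. Suppose a 10:10 list were used at enrolment and 10 of 20 then left at random. The remaining 10 would be 5:5 with probability C(10,5)²/C(20,10) = 63504/184756 = 34.4%, and 7:3 or worse with probability 33052/184756 = 17.9%.

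**The case against.** The best defence is that simple randomization is valid and that this is a pilot the Protocol says was not powered. The commonest split, 6:4, costs 4% in variance, and about two times in three the cost is no more than that. The mean of about +15% is driven by rare splits and is not what the study should expect. All of this stands. So does the point that precision loss and period bias are alternatives: an unadjusted within-patient mean has a variance that depends on N and not on the split, so its problem is bias only. Measuring change from each session's own T0 may also shrink the period effect, leaving only a period effect on the change itself.

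Three stronger readings are tempting but not supported.

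- **Open allocation.** A reader might infer it from "The study team member who makes these assignments will be aware of which patients are receiving active or sham stimulation". That sentence describes knowledge of assignments, not foreknowledge at enrolment, and independent draws cannot be predicted from earlier ones. The documents do not say whether this person also recruits, consents or schedules. What can be said is that concealment is not described.
- **Contaminated baseline.** A reader might fear that a known order affects the T0 measures. T0 is one of the outcome visits. The Sham protocol section keeps the outcome investigator blinded and away from TMS sessions, and the TWSTRS is scored from video by two blinded raters.
- **Early draw with later losses.** The Enrollment section mentions assignment after consent and examination, and says "Of those 20, we anticipate that 10 will enroll but later choose not participate in the study". That is narrative order, not a schedule, and it does not say whether people leave before or after the draw. Table 1 lists no randomization row, but its cell marks and Figure 1 were not legible in the text available, so neither is evidence on timing. As Step 5 shows, losses unrelated to order add no imbalance under the present rule.

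**Conclusion.** The point holds as a cheap improvement to a stated method. The even/odd rule leaves a 75.4% chance of unequal sequences and about a one-in-three chance of 7:3 or worse. At 7:3 the study either pays 19% in variance with period modelled or lets 0.4 of any period effect into the contrast without it. The typical loss is modest, and nothing here invalidates the randomization or the blinding of outcome assessment. The absence of a named period term in the SAP is what makes imbalance more than an efficiency matter.

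The figures assume independent 50:50 draws, 10 treated patients, departures unrelated to order and an additive period effect. The documents give no size for a period effect, so the bias can be stated only as a share of it.

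**What to change.** Replace the even/odd rule with a pre-generated, concealed list of 10 orders, 5 active-first and 5 sham-first, in random sequence. An existing team member who does not recruit, consent or assess should hold it. Release each order to the TMS operator only once that patient's S1:T0 measures are complete, so that people who leave earlier use no entry. Show this step in Table 1. Name period as a term in the SAP's model. If all 10 listed patients are treated, 5:5 is then certain; a patient lost after release would still disturb it.

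The cost is a wording change, one list in sealed envelopes or a locked file, and one residual degree of freedom for period (8 instead of 9 for the within-patient contrast). The downside is that the last orders become partly predictable to anyone who knows the earlier ones. The TMS operator is one such person and should therefore not decide enrolment either.

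The SAP is dated 7/21/2024 and written in the past tense, so allocation may already be complete. In that case, report the achieved split and include period in the model. It would also help to state when the draws were made and who held them.

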range of motion/excursion in six directions: up, down, left, right, left shoulder, right shoulder. Patients will also be instructed to perform arm movements while the EEG is recording. A sensor such as the Delsys system will be used to measure the patient's motion at the neck and head throughout this procedure. This portion of the study will be videotaped (Figure 2B and D).

Safety: Since the most important safety concern with rTMS is the possibility of seizure, participants with active seizure disorder or those at increased risk of seizure will be excluded. Low frequency protocols carry less risk of seizure as compared to high frequency protocols given that high frequency generates cortical excitability.³² In spite of the theoretically increased risk of seizure in accelerated rTMS protocols, several accelerated high-frequency protocols have been safely performed in other patient populations and have been tolerated well by patients without evidence of increased adverse events.²²⁻²⁴ The majority of these accelerated protocols are high-frequency stimulation, whereas our protocol calls for low-frequency stimulation which actually has an inhibitory effect and may actually be protective against seizures. A fuller review of accelerated rTMS protocols in a variety of different patient populations, with all adverse events listed can be found in the supplementary file included with this submission- it should be noted that the seizure risk was not greater in accelerated rTMS protocols compared to standard rTMS protocols. Other mild and transient side effects that participants may experience secondary to TMS include transient eye pain, toothache, muscle twitch, facial pain, neck stiffness, and pain or discomfort at the application site and skin.

Depression measure and suicide risk: If the Beck Depression Inventory reveals that the patient has feelings of harming themselves (Question 9 score 2 or above), we will refer them to mental health services available at Shands at the University of Florida.

Clinical Assessments:

Toronto Western Spasmodic Torticollis Rating Scale (TWSTRS): This is an objective scale evaluating patients on a variety of features including maximal excursion, duration, effects of sensory trick, shoulder elevation, range of motion, and time. This portion of the study will be videotaped.

Beck Depression Inventory (BDI): This is a 21-question survey evaluating depression in patients on a 0 to 3 scale.

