- Transient hearing threshold shift There is a possibility of temporary mild hearing loss due to the noise of the TMS machine. The rate of this risk is unknown yet. Earplugs will be provided to the participant to reduce the potential for this risk.
- Seizure A theoretical risk associated with brain stimulation. Since FDA clearance of TMS, the seizure risk is ≤0.1% per patient (less than 1 in 1000 patients). In the event that the participant has a seizure, the study staff will immediately stop the treatment session and make sure that the participant is safe during the seizure. The participant will be watched for a period of time after the seizure to make sure he or she is feeling well. Individuals with an active seizure disorder are excluded.
- Fainting Not directly related to magnetic stimulation. It is thought to be related to anxiety and psychophysical discomfort during the procedure. The laboratory is equipped, and staff is trained to respond to this risk if fainting occurs. However, the participant will be at very low risk (less than 1%) for fainting. Transfer to the emergency room might be needed if the participant fails to improve as expected.
- Effect of Magnetic Stimulation The NeuroStar TMS Therapy System is contraindicated for use in patients who have conductive, ferromagnetic, or other magnetic-sensitive metals implanted in their head within 30 cm of the treatment coil. Examples include cochlear implants, implanted electrodes/stimulators, aneurysm clips or coils, stents, bullet fragments, jewelry and hair barrettes. Failure to follow this restriction could result in serious injury or death. The NeuroStar TMS Therapy System is contraindicated for use in patients who have active or inactive implants (including device leads), including deep brain stimulators, cochlear implants, and vagus nerve stimulators. Contraindicated use could result in serious injury or death. To avoid these complications, participants with any of the above listed implanted objects will be excluded from this

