study.Childbearing Potential- There may be unknown risks to the fetus. Therefore, women of childbearing age will complete a pregnancy test for the TMS portion of the study at each visit. In order for the women of childbearing age to participate in this study, the participant should avoid becoming pregnant from their first day of most recent menses. A negative pregnancy test does not absolutely prove that a woman is not pregnant. If the female participant thinks that there is a possibility that she might be pregnant, the study team should be notified immediately. Nursing mothers are not eligible for participation in this project. The possibility exists that complications and undesirable side effects, which are unknown at this time, could occur.

EEG:

• A gel paste is used to attach the sensors during EEG which may mildly and briefly irritate the skin on the scalp or face. Hair products cannot be used on the day of testing (or should be washed out prior to testing), which may be inconvenient to the participant.

Possible Benefits: The participant may or may not benefit from taking part in the study. All participants will continue receiving botulinum toxin injections every 12 weeks as part of their standard of care. All patients will receive both active and sham rTMS; since the active rTMS is hypothesized to augment the effects of botulinum toxin injections, patients may experience further reduction in symptoms or sustained response to botulinum toxin. The information gathered from this study will benefit the neurology department and the larger research community as we continue to seek the most efficacious treatments for cervical dystonia.

Regulatory Approval and Statistics: The study will be approved by the University of Florida Institutional Review Board, and all subjects will provide written informed consent. The study is highly feasible given the relatively large number of patients with cervical dystonia that receive botulinum toxin injections on a regular basis. This is a pilot study so it has not been powered for statistical significance. We will use descriptive statistics and ANOVA to run analysis on the data that has been collected.

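### The numbered exclusion criteria omit increased seizure risk and nursing, both of which the protocol's safety and risk text says are excluded

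*Protocol*

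**What the plan says.** The protocol states who is excluded in three places.

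**Exclusion Criteria (Research Plan and Methodology).** There are four numbered items:

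1. Metal and stimulators, opening "Presence of metallic objects or neurostimulators in the brain" and followed by a bracketed set of examples that ends "aneurysm clips or coils, stents, bullet fragments, jewelry and hair barrettes), 2) pregnancy".
2. Pregnancy.
3. A seizure item, worded as "history of active seizures or epilepsy".
4. A gait item, covering marked scoliosis and similar problems that would rule out the walkway assessment.

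The list stops there. It has no general safety clause, no investigator-discretion clause and no pointer to the safety or risk text. The Inclusion Criteria cover age, injection schedule, duration of benefit and oral medication, and none of the points below.

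**Safety.** Seizure is named as the chief concern with rTMS, and the first safeguard given is that "participants with active seizure disorder or those at increased risk of seizure will be excluded".

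**Possible Discomforts and Risks.** The Seizure item says "Individuals with an active seizure disorder are excluded". The item on the effect of magnetic stimulation gives the device contraindication as magnetic-sensitive metal "implanted in their head within 30 cm of the treatment coil". It adds implants whether active or inactive, leads included, and says that participants with the objects listed there will be excluded. The childbearing text says "Nursing mothers are not eligible for participation in this project".

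The SAP says nothing about eligibility.

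**The concern.** Exclusions for safety should read the same wherever a protocol states them. Here the numbered list and the surrounding text give different answers for some patients, so two people screening the same patient from different sections could decide differently.

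The seizure wording carries most weight. The Safety paragraph concedes a theoretical rise in seizure risk with accelerated schedules, and the Background says that such schedules have not been studied in dystonia. Excluding people at increased risk is one of the safeguards the Safety paragraph offers, yet the numbered criteria do not contain it. Because the design is a crossover in which all 10 patients are to receive both conditions, anyone admitted is due to receive active stimulation.

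**Working it through.** No arithmetic applies, and the plan states no figure to reproduce. The check sets the statements side by side and asks, for each type of patient, which text excludes that patient.

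| Patient | Exclusion Criteria | Safety | Possible Discomforts and Risks |
|---|---|---|---|
| Active seizure disorder | Excluded | Excluded | Excluded |
| Past epilepsy, not now active | Excluded | Excluded only if this counts as increased risk | Not covered by the Seizure item |
| Raised seizure risk, no seizures or epilepsy | Not covered | Excluded | Not covered |
| Nursing, not pregnant | Not covered | Silent | Not eligible |
| Metal object or implant named as an example | Excluded | Silent | Excluded |
| Unnamed metal in the head outside the brain, or an unnamed implant or lead | Unclear | Silent | Contraindicated; exclusion depends on reading |

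**Seizure risk.** The Safety sentence joins two groups with *or*, so increased risk is a category beyond active disorder. The numbered list has no such category. The protocol does not define increased risk, so the medical history and neurological examination that it schedules have no stated criterion to apply. The Seizure item gives a third version, narrower than the numbered list because it does not mention a history of epilepsy.

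**Nursing.** The numbered list names pregnancy only. The pregnancy test in Table 1 and in the childbearing text would not identify a nursing woman who is not pregnant.

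**Metal and implants.** Every object named in the risks section is also named in the numbered list: cochlear implants, stimulators and electrodes, clips and coils, stents, bullet fragments, jewelry and barrettes. These are caught by both texts. What differs is the general wording: the list opens with the brain, while the risks section speaks of the head within 30 cm of the coil and of implants of any kind with their leads. Several of the list's own examples, such as jewelry, barrettes and vagus nerve stimulators, are not in the brain, so its opening phrase does not describe its own contents. On the other side, the exclusion sentence in the risks section refers back to objects listed above it, which may mean the named examples alone or the general categories too. The difference therefore matters only for objects or leads that neither text names.

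**The case against.** The strongest reply is that a protocol is read as a whole. The Safety and risks sections belong to the same document and use operative language, and every patient has a detailed history and examination. On that reading the two missing exclusions are in force and merely sit outside the list. This stands in part. The documents describe no screening form and do not say that the numbered list governs alone. A reader might infer that patients barred by the safety text would in fact have been enrolled; the documents do not show that. They also do not say that the later sections add to the list, and reading everything together does not settle which of three seizure wordings applies.

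A reader might also count metal as a third full gap and attach to it the protocol's warning of grave or fatal harm. That is not supported, because the named examples agree and the list plainly reaches beyond the brain. Nor is the list narrower throughout: on past epilepsy it goes further than the Seizure item.

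Finally, the Safety paragraph also rests on low-frequency stimulation, on earlier accelerated protocols and on a supplementary review of adverse events that is not in these documents. The risks section puts seizure risk at no more than 0.1% per patient. This tempers the likely harm. It does not remove the contradiction, since the same paragraph makes those arguments and still promises the exclusion.

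**Conclusion.** The point holds as an internal contradiction about who is excluded. There are two clear mismatches, on increased seizure risk and on nursing, with a third seizure wording that agrees with neither of the other two. There is one lesser wording difference on metal and implants, confined to unnamed objects or leads.

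The conclusion rests on the current protocol text alone and needs no assumption about how screening was done. How many patients are affected cannot be stated: the documents give no prevalence for seizure risk factors or nursing and leave increased risk undefined. No estimate, test or sample size depends on the point. It should be corrected because it bears on participant safety and on knowing which population was studied.

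**What to change.** Reconcile the Exclusion Criteria, the Safety paragraph and the relevant items under Possible Discomforts and Risks into one operative exclusion list used at screening. Each exclusion that the safety and risk text relies on should appear in the numbered criteria in the same words, or the safety and risk text should be changed to match the criteria. The reconciled text should use one seizure wording throughout, say what increased risk means if that category is kept, and use one description of metal and implants. Which version applies is for the investigator and the IRB.

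The SAP is dated 7/21/2024 and written in the past tense, so enrolment may be closed. If it is, the trial report should state which exclusions were actually applied.

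The cost is a minor wording amendment with no new procedure, and possibly slightly fewer eligible patients.
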